14.1 Primary Objectives

- 1. To determine if a volume of 500 microlitres to 1.1 millilitre of blood can be collected after a single lancing of the fingertip with gentleheel®.
- 2. To assess pain from fingertip lancing with gentleheel®.

14.2 Secondary Objectives

Reporting of adverse events.

15 Study Design, Data Collection and Data Analysis

15.1 Recruitment and baseline assessments

When the Investigator has determined the eligibility of a specific subject as per the defined inclusion and exclusion criteria, the Investigator or a person designated by the Principal Investigator who has been trained on the Clinical Investigation Plan, will explain the nature and scope of the clinical investigation, potential risks and benefits of participation, and answer any question of the patient. The patient will be provided ample time to read and understand the Informed Consent Form and to consider his/her participation in the study. If the patient agrees to participate, the informed consent form must be signed and personally dated by the patient. The Investigator must also sign and date the Informed Consent Form, prior to enrolment of the patient. The Investigator will maintain a copy of the relevant study approval along with a copy of each patients signed Informed Consent Form in a designated study file. The investigator will provide patients with a copy of their signed Informed Consent Form. If new information about the clinical study becomes available, the patients will be notified by the Principal Investigator or study personnel. If the approving committee of the study requires an updated Informed Consent Form to be administered, all actively participating subjects will sign the new form.

After the subject signs the Patient Consent Form, he/she is considered enrolled into the study.

15.2 Randomisation and blinding

Since this is a prospective, interventional, non-randomised study, no randomisation will be necessary. As only one device will be used there will be no need for blinding.

15.3 Investigation Design

IRAS Number: 311621

A sample size of 50 patients will be used. Each patient will perform two separate incisions on the middle and ring fingers, resulting in 100 blood draws. During the procedure, the following data will be documented:

- the location of the incisions (which finger middle/ring and which side of the fingertip ulnar/radial).
- the volume of blood obtained from each incision;
- the pain level experienced for each incision;

After appropriate explanation of the procedure to the patient, he/she will sign the Informed Consent Form to confirm that their participation in the study is voluntary. All required data as per the CRF will be obtained and the patient will then collect blood from 2 incisions on his/her fingertips.

All collected blood samples will be used for volume measurement and discharged afterwards. Following the blood collection from all 2 incisions, the patient will be appropriately monitored, until he/she leaves the investigational site. Any adverse event if presented will be documented before the patient leaves the investigational site.

Please see Table 1 for an overview of the data being collected for each subject on the day of the blood collection procedure.

Table 1: Overview of the data to be collected for each subject in the day of the blood collection procedure.

Incision #	Finger identification (middle/ring)	Incision position (radial/ulnar)	Volume of blood collected (µI)	Pain level (0 to 10)
1				
2				

Within 5 days of procedure, a follow-up telephone call will take place in order to assess if any adverse events occurred.

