15.5 Procedure for Capillary Sampling

This protocol is based on the recommendations set out by the WHO guidelines on drawing blood: Capillary blood sampling (6). A patient information sheet will be provided to the patient with written instruction on how to use the device.

Material Required

The following materials will be provided with gentleheel®:

- Alcohol wipe
- Sterile gauze pads
- Blood collection container, with marker lines to indicate the volume of blood collected

Preparation

IRAS Number: 311621

- Wash your hands under warm water for 2 minutes.
- While standing up swing your arms several times to stimulate the blood flow.
- Use the alcohol wipe to clean the finger you intend to use we recommend using the middle or ring finger of your non-dominant hand.

Procedure for sample collection

 When making an incision on the adult's finger, the incision site must be on the fingertip (see illustration below), and indicated as radial/ulnar.

[figure not shown]

Figure 2: Illustration of the incision site in an adult fingertip.

- Remove gentleheel® from its packaging.
- Remove the trigger lock. Once the trigger is removed, do not depress the trigger or place anything in front of the opening at the base of the device.
- **Incision.** Place the opening (at the base of the device) against the cleansed incision site ensuring that the base of the device is flush with the fingertip's skin. After depressing the trigger, immediately remove the device.
- Remove first drop of blood. The first drop of blood should be wiped away from the incision with a dry sterile gauze pad.
- **Collect sample.** A second drop of blood should form over the incision site. Collect the blood sample and fill it in the collection container provided. Avoid squeezing the finger too tightly. Fill both blood tubes to the fill line.
- **Compression.** When the blood collection procedure is complete, apply firm pressure to the site to stop the bleeding using the dry sterile gauze pad provided.
- Note down your perception of pain on a scale of 0-10, with 0 being no apin and 10 the worse imaginable pain.

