15.9 Withdrawal Criteria

IRAS Number: 311621

Patients have the right to withdraw from the study at any time and for any reason without prejudice to their future medical care by the investigation team or investigation site. The Investigator will record all information regarding the subject discontinuation. A patient may be

withdrawn from the study for the following reasons, and data until the date of withdrawal will be recorded in the Case Report Form (CRF):

- Subjects may choose to withdraw from the study under the terms of the Declaration of Helsinki and their consent documentation without having to give a reason;
- Any unanticipated adverse event which is, in the opinion of the Investigator, related to the treatment and will endanger the well-being of the patient if treatment is continued;
- Development of any intercurrent illness(es), infection or condition(s) that might interfere with the protocol;
- Non-compliance with the clinical investigation procedures deemed by the Investigator to be sufficient to cause discontinuation;
- Any problem deemed by the Investigator to be sufficient to cause discontinuation.

16 Statistical Considerations

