16.1 Sample Size

Considering the design and objective of this investigation, the nature of the results needed to conclude on the safety and performance of gentleheel® as incision device for adult fingertips, and the fact that the device is already CE-marked as heel incision device for new-born sampling, the inclusion of 50 subjects in the investigation, a 2 incisions per subject, which will result in 100 blood draws to be assessed, appears therefore sufficient to obtain conclusive findings. This was based on the precision of the 90% CI for the primary objectives as this is a single-arm study. Under this approach, no statement of power is required and alpha = 0.10 will be used as the CI specified as a two-sided 90%.

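### Two self-incisions per subject in one sitting are counted as 100 equivalent draws, with no set finger order, for an objective about a single lancing by a lay user

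*Protocol*

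**What the plan says.** Section 14.1 of the protocol sets two primary objectives: whether a stated volume "can be collected after a single lancing of the fingertip with gentleheel", and how painful the lancing is. Section 13 asks whether lay people can use the device without help from medically qualified staff.

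Section 15.3 sets the design: "Each patient will perform two separate incisions on the middle and ring fingers, resulting in 100 blood draws". Finger, side, volume and pain are recorded for each incision, and Table 1 has a numbered row for each. The synopsis in Section 23 allows 20 minutes for the procedure.

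No order is set. Section 15.2 says that randomisation is not needed, and Section 15.5 gives the subject only advice: "we recommend using the middle or ring finger of your non-dominant hand".

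Section 16.1 justifies the size by the number of draws, "which will result in 100 blood draws to be assessed, appears therefore sufficient to obtain conclusive findings", and adds: "This was based on the precision of the 90% CI for the primary objectives as this is a single-arm study". The level is fixed by "alpha = 0.10 will be used as the CI specified as a two-sided 90" per cent. Section 16.3 presents the primary objectives as a proportion with a 90% interval and does not say whether the denominator is draws or subjects.

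Under Section 15.9 a subject may withdraw at any time, and "data until the date of withdrawal will be recorded in the Case Report Form (CRF").

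**The concern.** Incision 1 is the subject's first use of the device in the study. Incision 2 is made minutes later by someone who has just done it once. Practice could make the second attempt better; residual pain or anxiety could make it worse. A subject who does badly at incision 1 may also not make incision 2, so second draws could come more often from subjects whose first attempt went well.

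If all draws are counted alike, the resulting proportion or pain summary mixes first and repeat use. It may not describe a lay person lancing for the first time. With no set order, finger and attempt can also be mixed: if most subjects start with the same finger, a difference between attempts cannot be told from a difference between fingers. The analysis can be specified later, but finger order cannot be assigned after the data are collected.

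**Working it through.** **The plan's own count.** 50 subjects × 2 incisions = 100 draws, as stated. The precision argument in Section 16.1 cannot be reproduced, because it gives no target width, expected proportion or within-subject correlation.

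**Precision.** The inputs are the two-sided 90% level (z = 1.645), 50 subjects and 100 draws. The half-width is z × √[p(1 − p)/n]. For two draws per subject with within-subject correlation ICC, the variance is multiplied by (1 + ICC). The values of p and ICC are assumed.

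| p | 100 draws taken as independent | Both draws, ICC 0.5 | Incision 1 only (n = 50) |
|---|---|---|---|
| 0.5 | 8.2 points | 10.1 | 11.6 |
| 0.8 | 6.6 | 8.1 | 9.3 |
| 0.9 | 4.9 | 6.0 | 7.0 |

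At p = 0.5: 1.645 × √(0.25/100) = 0.082; 1.645 × √(0.25 × 1.5/100) = 0.101; 1.645 × √(0.25/50) = 0.116. The effective number of draws, 100/(1 + ICC), is 83, 67 and 56 for ICC 0.2, 0.5 and 0.8.

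**Shift from an order effect.** Let p1 and p2 be the success rates at incisions 1 and 2, both assumed. If nobody stops, the pooled rate is (p1 + p2)/2, so it differs from p1 by (p2 − p1)/2:

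- 0.60 then 0.70: pooled 0.65, shift +5 points.
- 0.60 then 0.80: pooled 0.70, shift +10 points.
- 0.60 then 0.50: pooled 0.55, shift −5 points.

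**Shift from selective stopping.** Let s be the assumed share of subjects with a failed first draw who make no second one, and ρ the assumed correlation between a subject's two results. The chance of success at both attempts is p11 = p1·p2 + ρ√[p1(1 − p1)p2(1 − p2)], and of failure then success p01 = p2 − p11. The pooled rate is [p1 + p11 + p01(1 − s)] / [1 + p1 + (1 − p1)(1 − s)].

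- p1 = p2 = 0.60, ρ = 0.5: p11 = 0.36 + 0.12 = 0.48 and p01 = 0.12. With s = 0.2, 1.176/1.92 = 0.613 (+1.3 points, 96 draws). With s = 0.5, 1.14/1.80 = 0.633 (+3.3 points, 90 draws).
- The same with ρ = 0: the shift is zero for any s.
- p1 = 0.60, p2 = 0.70, ρ = 0.5, s = 0.5: p11 = 0.532 and p01 = 0.168, so 1.216/1.80 = 0.676 (+7.6 points). By normal approximation, a nominal 90% interval that takes the draws as independent covers the first-attempt rate about 53% of the time.
- p1 = 0.60, p2 = 0.50, ρ = 0.5, s = 0.5: pooled 0.590 (−1.0 point). Here stopping largely offsets the order effect.

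**Pairing alone.** With no order effect, no stopping and ρ = 0.5, the interval that takes 100 draws as independent covers about 82% rather than 90%.

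**The case against.** Several points on the other side stand.

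- **Pooling is not stated as the analysis.** The 100 draws appear in the design and the sample-size reasoning. Section 16.3 gives no denominator, and an analysis plan that is not shown may define one. That silence alone is no fault of the protocol.
- **Each draw is itself the volume after one lancing.** Elsewhere the protocol contrasts one puncture with several, and no section limits the question to first-ever use. First use is a natural reading of the lay-user question, but not the only one.
- **Confounding is partial.** Finger and side are recorded and no objective compares them. If subjects vary their order, finger and attempt are only partly mixed.

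Three stronger readings are tempting but not supported:

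- A reader might infer that warming is lost before incision 2, because "Wash your hands under warm water for 2 minutes" appears once. Section 15.5 can be read as instructions for each collection; unpacking the device and wiping away the first drop are also listed once.
- A reader might infer that reasons for stopping go unrecorded. Section 15.9 already has the investigator record the information on a discontinuation.
- A reader might infer that the results will be too favourable. No rate, order effect or stopping frequency is given, and the shift can go either way.

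None of this removes the core: the plan counts a first and a repeat attempt as equivalent and leaves finger order open.

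**Conclusion.** The point holds as a design weakness that is cheap to mend. It is not a demonstrated bias. Sections 15.3 and 16.1 count first and second attempts as 100 equivalent draws for an objective about a single lancing. A summary over all draws may therefore fail to describe a first-time lay user.

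Under the assumed scenarios above, the pooled proportion departs from the first-attempt rate by between −5 and +10 points, against a nominal half-width of about 8 points at p = 0.60. Stopping alone matters only if a subject's two results are correlated. The same reasoning applies to pain, where the direction is equally open. Because Table 1 numbers the incisions, a first-incision analysis remains possible from the data already planned; the protocol simply does not commit to it.

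**What to change.** - **Section 16.3:** give volume success and pain separately for incision 1 and incision 2, using the numbering in Table 1. Take incision 1 (n = 50, one per subject) as the estimate for first lay use, and report the within-subject difference between incisions.
- **Section 16.3:** any figure that combines both draws should respect the pairing and show how many second incisions were not done.
- **Section 15.3:** assign which finger is lanced first by odd or even subject number. This separates finger from attempt. It does not remove a practice effect, which the separate reporting deals with.

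The cost is protocol wording and one allocation line on the CRF, with no added subjects, visits or measurements. The price is the wider interval for incision 1 alone. At p = 0.5 this is 11.6 − 8.2 = 3.4 points against the nominal figure, but only 11.6 − 10.1 = 1.5 points against a paired analysis of both draws at an assumed ICC of 0.5.

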15.4 Table Summary of Key Timelines

Data	Recruitment	Procedure	Telephone Follow up
Collected	Up to 4 weeks pre- procedure	Day 0	Day 5
Informed consent	Х	X	
Blood volume collection		Х	
Pain score		Х	
Adverse events (CRF's)		Х	Х

15.5 Procedure for Capillary Sampling

This protocol is based on the recommendations set out by the WHO guidelines on drawing blood: Capillary blood sampling (6). A patient information sheet will be provided to the patient with written instruction on how to use the device.

Material Required

The following materials will be provided with gentleheel®:

- Alcohol wipe
- Sterile gauze pads
- Blood collection container, with marker lines to indicate the volume of blood collected

Preparation

IRAS Number: 311621

- Wash your hands under warm water for 2 minutes.
- While standing up swing your arms several times to stimulate the blood flow.
- Use the alcohol wipe to clean the finger you intend to use we recommend using the middle or ring finger of your non-dominant hand.

Procedure for sample collection

 When making an incision on the adult's finger, the incision site must be on the fingertip (see illustration below), and indicated as radial/ulnar.

[figure not shown]

Figure 2: Illustration of the incision site in an adult fingertip.

- Remove gentleheel® from its packaging.
- Remove the trigger lock. Once the trigger is removed, do not depress the trigger or place anything in front of the opening at the base of the device.
- **Incision.** Place the opening (at the base of the device) against the cleansed incision site ensuring that the base of the device is flush with the fingertip's skin. After depressing the trigger, immediately remove the device.
- Remove first drop of blood. The first drop of blood should be wiped away from the incision with a dry sterile gauze pad.
- **Collect sample.** A second drop of blood should form over the incision site. Collect the blood sample and fill it in the collection container provided. Avoid squeezing the finger too tightly. Fill both blood tubes to the fill line.
- **Compression.** When the blood collection procedure is complete, apply firm pressure to the site to stop the bleeding using the dry sterile gauze pad provided.
- Note down your perception of pain on a scale of 0-10, with 0 being no apin and 10 the worse imaginable pain.

15.6 Procedure

IRAS Number: 311621

After appropriate explanation of the procedure to the patient, he/she will sign the Informed Consent Form to confirm that their participation in the study is voluntary. All required data as per the CRF will be obtained and the patient will then collect blood from 2 incisions on his/her fingertips. No more that a maximum of 4 ml of blood will be collected per patient. The patient will then be asked to rate their pain using the Numerical Pain Rating Scale of 0-10, with 0 being no pain and 10 the worse imaginable pain.

All collected blood samples will be used for volume measurement and discharged afterwards. Following the blood collection from all 2 incisions, the patient will be appropriately monitored, until he/she leaves the investigational site. Any adverse event if presented will be documented before the patient leaves the investigational site.

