22.1 Adverse Events and Device Deficiency Recording on the CRF

All AE must be reported for each patient with a full description, including the nature, the date of onset and resolution, the determination of seriousness, the severity, the action taken, the corrective treatment and the relationship to the device and/or procedure assessed by the Investigator. All investigational device deficiencies will be documented on the CRF and reported to Sponsor.

23 Protocol Synopsis

Title of the investigation: Evaluation of the GRI gentleheel® incision device for adult blood sampling Intended Use Extension				
Objective:	The objective of the proposed clinical investigation is to evaluate the safety and performance of the gentleheel® incision device for capillary blood sampling in adults' fingertips.			
Intended Use:	The gentleheel® device as a fingertip incision device intended for blood sampling in adults.			
Investigational Device:	gentleheel® model Toddler, Blue Incision depth 2.00 mm Incision length 3.00 mm			
Investigation Design:	Prospective, interventional, non-randomized, single-centre			
Participating Sites:	1 site in the UK			
Planned Number of Patients:	50 patients			
Sample size	100 blood draws, 2 finger incisions per patient			
Participation Duration:	Procedure: 20 minutes Follow-up: 5 days (Telephone Call)			
Total estimated duration of the investigation:	1 Month			
Outcomes:	Primary Objectives:			
	 Determine the capillary blood volume collected after a single lancing of the fingertip. Assessment of pain during finger incision using the 0-10 Numerical Pain Rating Scale Secondary Objectives: Adverse events. 			
Inclusion Criteria:	Subjects older than 18 years (adults)Subjects able to provide informed consent			

Exclusion Criteria:

- Subjects younger than 18 years
- Subjects unable to provide informed consent
- Subjects with cognitive impairment which is sufficient to adversely affect the participants understanding of the study, their ability to respond to patient questionnaires or their ability to cooperate with post-procedure assessment.
- Subjects who may be dehydrated
- Subjects diagnosed with poor peripheral circulation from other causes
- Subjects who present with a callus, skin ulceration, or blister at the intended puncture site
- Subjects with thrombocytopenia and/or Platelet abnormalities
- Subjects diagnosed with peripheral edema. Pregnancy or breastfeeding (self-reported)
- Confirmed or suspected malignant cancer

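### The timing and reference period of the primary pain rating are inconsistent across the synopsis and sections 15.3, 15.5 and 15.6

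*Protocol*

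**What the plan says.** The protocol describes the pain measurement in five places.

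- Section 14.1 makes pain the second primary objective: "To assess pain from fingertip lancing with gentleheel". It gives no time point.
- The synopsis (section 23) lists the outcome as "Assessment of pain during finger incision using the 0-10 Numerical Pain Rating Scale". The reference period is the incision.
- Section 15.3 requires the record to show "the pain level experienced for each incision", and Table 1 has a pain column with separate rows for incisions 1 and 2.
- Section 15.5, the instructions that the participant follows, ends with "Note down your perception of pain on a scale of 0-10". This comes after the steps for incision, wiping away the first drop, collection and compression.
- Section 15.6 says that "the patient will then collect blood from 2 incisions on his/her fingertips" and then, after a limit on total blood volume, "The patient will then be asked to rate their pain using the Numerical Pain Rating Scale of 0-10". It does not say whether the rating is given once or for each finger.

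The timelines table in section 15.4 places the pain score on Day 0 and is no more precise than that.

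**The concern.** A pain score means little until it is fixed which pain is rated and when. Here the outcome is named as pain during the incision, but neither operational section asks about it in those terms or at that point. Section 15.5 asks for a general perception of pain once the sampling sequence is over. Section 15.6 places the rating after both fingers have been sampled.

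Two consequences follow. A participant asked at the end of 15.6 has to recall the first finger after the second has been lanced, so the newer pain can colour the older score. And with no reference period stated, the answer can take in discomfort from squeezing or compression. The protocol itself separates these phases: section 19 lists pain both during and after the procedure as an anticipated adverse event, and section 15.5 cautions against squeezing too hard. A score that absorbs later pain therefore overlaps with the secondary, adverse-event objective.

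This cannot be left to the analysis plan. If the incisions were not rated separately and with a clear reference, no analysis can recover those scores.

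**Working it through.** **Planned number of scores.** Sections 15.3 and 16.1 give 50 patients and 2 incisions each: 50 × 2 = 100 draws. This reproduces the protocol's figure. Section 15.3 and Table 1 attach one pain score to each draw, so 100 pain scores are planned.

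**The passages side by side.**

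| Place | What is rated | When | How many |
|---|---|---|---|
| Synopsis (section 23) | Pain during the incision | Not stated | Not stated |
| 15.3 and Table 1 | Pain of each incision | Not stated | One per incision |
| 15.5 | Pain, unspecified | After collection and compression | Not stated |
| 15.6 | Pain, unspecified | After collection from both incisions | Not stated |

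**Step 1: 15.5 against 15.6.** If 15.5 is carried out once per finger, finger 1 is rated before finger 2 is lanced, whereas 15.6 puts all rating after both collections. These are different moments for finger 1. If 15.5 is instead carried out once for the whole session, which its mention of two tubes leaves open, the order agrees with 15.6, but then finger 1 is rated late under both sections.

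**Step 2: how many scores are affected.** Under a literal 15.6 all 100 scores are given after collection. One per patient, 50 × 1 = 50 of the 100, refers to a finger after which another has already been lanced.

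**Step 3: reference period.** Only the synopsis and 15.3 with Table 1 tie the score to the incision. The two sections that govern what the participant is asked do not.

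**Step 4: what a misreading would cost in precision.** This is an illustration, not a description of the plan. Section 16.3 reports the primary objectives as proportions with 90% confidence intervals. Taking an assumed proportion of 0.5 and z = 1.645, the half-width is 1.645 × √(0.25/n):

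- 100 independent scores: 0.082, or 8.2 points.
- 50 scores, one per patient: 0.116, or 11.6 points.

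Two scores from one patient will be correlated, and the protocol gives no value. With effective n = 100/(1 + ρ) and assumed ρ of 0.3, 0.5 and 0.8, effective n is 77, 67 and 56, and the half-widths are 9.4, 10.1 and 11.0 points. Even if 15.6 were misread as one pooled score, the loss of precision would be limited, and smaller the more a patient's two scores agree. The main issue is what the score measures.

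**The case against.** The case on the other side is substantial.

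*The number of scores is not in conflict.* Section 15.3 and Table 1 fix one per incision. Section 15.6 is silent on number, requires all CRF data to be obtained, and is compatible with two ratings given at the end. This stands. A reader might infer that 15.6 orders a single pooled score, giving 50 scores where 100 are needed, or one value copied into both rows of Table 1. The text does not say so. It is a possible misreading, made easier because 15.6 omits the per-incision wording.

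*Naming the pain is not the same as timing the record.* A participant lancing their own finger cannot write down a score at that instant, so recording it shortly afterwards does not contradict the synopsis. This stands in part. A later record would be acceptable if the question pointed back to the incision, but neither 15.5 nor 15.6 does that. That the score mixes incision with squeezing and compression is a risk, not an established fact.

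*Sites and delay.* A reader might fear that sites would follow different sections. This is a single-centre study with a study coordinator and planned training in data collection, so that does not arise. A reader might also take the 20-minute procedure time in the synopsis as the recall delay. That time covers the whole procedure, including preparation such as two minutes of hand washing, and is not broken down by step. No lancing-to-rating interval can be derived.

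*A pause before collection could harm the other primary outcome.* Blood volume is measured from the same incision, and a stop for rating just after lancing could disturb collection. This stands and shapes the remedy.

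What remains after these points is that 15.6, read as written, rates finger 1 after finger 2 has been lanced, and that the reference period is missing from both operational sections.

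**Conclusion.** The point holds as an inconsistency of timing and reference period in a primary endpoint. It rests on the wording of 15.5 and 15.6 alone and needs no numerical assumption. If 15.6 is followed literally, 50 of the 100 planned scores are recalled after a second lancing, and all 100 are given after collection without a stated reference to the incision. Neither the direction nor the size of the resulting bias can be worked out from the protocol. The interval widths shown above depend on an assumed proportion and assumed correlations, and illustrate only a misreading that the protocol does not prescribe.

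The defect is modest and easily corrected, but should be dealt with before enrolment, because a score taken at the wrong time or about the wrong pain cannot be repaired later.

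**What to change.** Align section 15.5, section 15.6 and the participant's instruction sheet with section 15.3, Table 1 and the synopsis:

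1. Each incision receives its own 0 to 10 score, entered in its own row of Table 1.
2. The score for the first incision is recorded before the second incision is made.
3. Each score is recorded as soon after lancing as is practical without disturbing blood collection. A stop before collection should not be mandated.
4. The question asks explicitly about pain from the incision itself.
5. If pain of collection or compression is also of interest, it is recorded as a separately named score.

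The cost is a change of wording and a brief pause between fingers, with no added visit. The change does not remove every carry-over: the second finger is still rated by someone who has just experienced the first. Table 1 already records incision order, so this can be examined.
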